5.3 STRATEGIES FOR RECRUITMENT AND RETENTION

Pregnant women presenting to an obstetrical ultrasound unit or those women on labor and delivery who are not in active labor at or beyond 36 weeks EGA will be approached for enrollment in the study. Women from all ethnic backgrounds will be approached to participate. The actual percentage of minority patients will not be known until patient recruitment is completed. It is expected that there the study population will include adequate representation from a large variety of ethnic groups.

Study subjects are only being asked to undergo two additional measurements during ultrasound after they consent to the study, and we anticipate that this additional work will take no more than 5 minutes of the subject's time. Subjects will not be compensated for participating in the study.

Target sample size is for 3,000 women to enroll, which will give approximately 300 women with CPR < 10th percentile for gestational age.

Accrual rate will depend upon the number of sites participating in the research. There are currently 36,000 deliveries annually within the consortium.

No advertisements to potential study subjects are planned.

5.4 PARTICIPANT WITHDRAWAL OR TERMINATION

5.4.1 REASONS FOR WITHDRAWAL OR TERMINATION

An subject may request that she be withdrawn from the study. If ultrasound has already been performed, she may request that her data not be used and that data not be abstracted from her clinical record.

An investigator may termination participation in the study if the participant meets an exclusion criterion (which may be newly developed that precludes further participation in the study.

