5.2 PARTICIPANT EXCLUSION CRITERIA

- Multifetal pregnancy at the time of presentation

- Known fetal chromosomal anomaly
- Known fetal malformation
- Preeclampsia
- Fetal growth restriction
- Prior cesarean section
- Placental abnormalities such as previa or accreta
- Pregestational diabetes

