5.4.2 HANDLING OF PARTICIPANT WITHDRAWALS OR TERMINATION

Participant withdrawals will be recorded and described in the final report of the study. Study data generated by a patient who has withdrawn will not be included in the final study of CPR effects on either the primary or secondary outcome variables.

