9.5 SAMPLE SIZE

To determine sample size we assumed a 20% cesarean rate for those women who have a CPR <10th percentile and a 10% cesarean rate in women with a CPR ≥10th percentile. With 90% power to detect a difference and $\alpha = 0.05$, 288 subjects with a CPR <10th percentile will need to be enrolled into the study. This means approximately 3,000 subjects will need to be screened.

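### Section 5.4 lets investigators terminate women for conditions that arise after the CPR is measured and has no rule keeping their outcomes, so the primary comparison can be biased by an unknown amount in either direction

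*Protocol*

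**What the plan says.** Protocol 5.4.1 gives two ways out of the study. A woman may ask to be withdrawn and, if the ultrasound has been done, "she may request that her data not be used". Separately, an investigator may end her participation "if the participant meets an exclusion criterion (which may be newly developed that precludes further participation in the study". No time limit and no criterion for using this discretion are given.

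The exclusion list in 5.2 includes preeclampsia and "Fetal growth restriction". Either can first appear after enrollment.

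Section 5.4.2 covers withdrawals and termination in its heading. Its body states: "Study data generated by a patient who has withdrawn will not be included in the final study of CPR effects", and applies this to primary and secondary outcomes alike. The body does not mention women terminated by an investigator, and no other section says that their data are kept.

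On timing, 6.3.1 places the Doppler directly after consent. Sections 6.3.3 and 6.3.4 describe one visit, with everything else taken from charts after delivery. The synopsis gives a participant duration of 1 day to 6 weeks. Section 6.3.2 has its own check that the fetus is not growth restricted at the enrollment scan.

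**The concern.** The exposure is fixed when the CPR is measured, and the outcome comes at delivery. A rule that removes women for something that happens in between is selection after exposure. It does no harm if the reason for removal is unrelated to exposure and outcome, but that cannot be assumed here. Section 2.1 presents the CPR as a marker of placental insufficiency in fetuses that look normally grown. Growth restriction and preeclampsia that emerge later are plausible expressions of the same process, and both can lead to cesarean.

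Four things are at stake:

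- **The primary comparison.** The cesarean rates in the low-CPR group and in the other women can both be altered, by different amounts.
- **Several secondary outcomes in 4.2.2.** Birthweight percentile, small babies missed before birth and NICU admission are close to the reason for removal.
- **Consistency across sites.** Removal is optional. Outcomes are read from charts after delivery (6.1.2), so a new condition might be noticed when the mode of delivery is already visible. Section 2.3.1 also allows an exception to blinding for pregnancies judged to be at high risk.
- **The question answered.** The objective in section 3 is prediction from a scan after 36 weeks. At that scan nobody knows who will later develop an exclusion condition.

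The group tests in 9.1 do not correct for such selection, and outcomes that are never abstracted cannot be recovered later.

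**Working it through.** **1. When the clause can act.** Consent and Doppler are consecutive (6.3.1), and growth restriction at that scan is handled in 6.3.2. Almost no interval before the Doppler remains in which a condition could newly develop. The clause therefore acts mainly between Doppler and delivery, when the only participation left to end is chart abstraction.

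**2. The plan's own figure.** Inputs from 9.5: "we assumed a 20% cesarean rate for those women who have a CPR <10th percentile", "a 10% cesarean rate in women with a CPR ≥10th percentile", 90% power, α = 0.05 (two-sided assumed). With equal groups and mean rate 0.15:

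n = [1.96·√(2·0.15·0.85) + 1.2816·√(0.20·0.80 + 0.10·0.90)]² / 0.10² = (0.990 + 0.641)² / 0.01 ≈ 266.

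The continuity correction, n/4·[1 + √(1 + 4/(n·0.10))]², gives 286, close to the stated 288. That figure is not disputed. The 20% and 10% serve below as the rates with every woman kept: risk difference (RD) 10.0 points, risk ratio (RR) 2.00.

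**3. Effect of removal.** Let x be the share of a group removed, c the cesarean rate among those removed and p the group's full rate. The analysed rate is (p − x·c)/(1 − x). The documents give neither x nor c, so every value below is an assumption. Group sizes start from about 300 low-CPR women out of 3,000 (5.3).

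| x low / other | c | Low CPR | Other | RD (points) | RR |
|---|---|---|---|---|---|
| none | – | 20.0% | 10.0% | 10.0 | 2.00 |
| 3% / 3% | 40% | 0.188/0.97 = 19.4% | 0.088/0.97 = 9.1% | 10.3 | 2.14 |
| 5% / 5% | 40% | 0.180/0.95 = 18.9% | 0.080/0.95 = 8.4% | 10.5 | 2.25 |
| 5% / 3% | 40% | 0.180/0.95 = 18.9% | 0.088/0.97 = 9.1% | 9.9 | 2.09 |
| 5% / 2% | 40% | 0.180/0.95 = 18.9% | 0.092/0.98 = 9.4% | 9.6 | 2.02 |
| 10% / 3% | 40% | 0.160/0.90 = 17.8% | 0.088/0.97 = 9.1% | 8.7 | 1.96 |
| 15% / 5% | 50% | 0.125/0.85 = 14.7% | 0.075/0.95 = 7.9% | 6.8 | 1.86 |
| 20% / 5% | 40% | 0.120/0.80 = 15.0% | 0.080/0.95 = 8.4% | 6.6 | 1.78 |

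**4. Direction.** Removal lowers a group's rate by x(c − p)/(1 − x). With c = 40% this is 0.20·x/(1 − x) in the low-CPR group and 0.30·x/(1 − x) in the other. The RD therefore shrinks only if the odds of removal in the low-CPR group exceed 0.30/0.20 = 1.5 times those in the other group. With equal removal it grows to 10/(1 − x), for example 10/0.97 = 10.3. RD and RR can also move in opposite directions, as in the 5%/3% row.

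**5. Power.** Power = Φ[(RD − 1.96·SE₀)/SE₁], with SE₀ pooled and SE₁ unpooled. With 300 v 2,700 and no removal it is 99.6%. For 15%/5% and c = 50%, 255 v 2,565 women remain, SE₀ = 0.0183 and SE₁ = 0.0228, so Φ[(0.0681 − 0.0359)/0.0228] = Φ(1.41) ≈ 92%. For 10%/3% and c = 40% it is 98%. The extreme 20%/5% row gives about 88%.

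**The case against.** The strongest reply is that the two rules are not expressly joined. Section 5.4.1 separates a woman's withdrawal from an investigator's termination, and the body of 5.4.2 speaks only of withdrawn patients. A reader might infer that 5.4.2 expressly discards terminated women's data. The text does not say that. The inference rests on the heading, on the absence of any rule that keeps those data, and on chart abstraction being the only activity left to stop. This point stands as a limit on how the finding is worded. It does not remove the finding, because on either reading the outcome is likely to be missing.

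A second reply is that the clause is meant for exclusions revealed by the enrollment scan. That fits 6.3.2 and the fact that no later eligibility check is scheduled. But a finding at the scan is already covered there, and the reference to newly developed criteria reaches further. If the narrow meaning is intended, the text should say so.

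Third, small babies missed before birth are a secondary outcome, and some women enter at induction with little time to develop anything new. Both points stand and suggest that the number affected may be small. Neither bears on late preeclampsia in women scanned weeks before delivery.

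Fourth, a reader might infer that the low-CPR effect must be understated, or that as many as 60 of 300 low-CPR women would be lost. The documents support neither. The comparator's rate falls too and the direction depends on the inputs. The 60 is only an assumed 20% multiplied by 300, with every eligible removal carried out.

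**Conclusion.** The concern holds as a stated rule that permits discretionary selection after exposure, on conditions related both to what the CPR is meant to mark and to cesarean. It is more than missing detail, because it affects who enters the primary comparison.

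The size and direction of the bias are not determined by the documents. In the scenarios shown, RD ranges from 6.6 to 10.5 points against 10.0, and RR from 1.78 to 2.25 against 2.00. The bias is toward the null if removals concentrate in the low-CPR group and slightly away from it if removal is equal. These ranges rest on assumed removal shares, an assumed cesarean rate common to removed women in both groups, and the 20% v 10% of 9.5.

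Loss of power is not a supportable reading. Because the real split is about 1:9, power stays at or above 92% except in the most extreme row, where it is about 88%. The damage is to the estimate and to whom it applies.

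A smaller inconsistency stands beside this: 5.4.1 makes non-use of data something a woman may request, while 5.4.2 applies it to everyone who has withdrawn.

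**What to change.** - **In 5.4.1,** apply the exclusion criteria only up to the completed Doppler, keep the growth check at the enrollment scan in 6.3.2, and delete study termination for conditions that develop later.
- **In 5.4.2,** keep every woman with a valid CPR in the primary and secondary analyses unless she asks that her data not be used. This also reconciles 5.4.2 with 5.4.1.
- **At abstraction,** record later preeclampsia or growth restriction as descriptors by CPR group, and exclude these women only in a sensitivity analysis.

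The cost is two sentences of protocol text. The outcomes come from chart abstraction that is already planned, with no further contact with participants and no change to clinical care. If any women have already been terminated under the current wording, they should be counted by CPR group and, where consent allows, their outcomes abstracted.

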5.4.2 HANDLING OF PARTICIPANT WITHDRAWALS OR TERMINATION

Participant withdrawals will be recorded and described in the final report of the study. Study data generated by a patient who has withdrawn will not be included in the final study of CPR effects on either the primary or secondary outcome variables.

5.5 PREMATURE TERMINATION OR SUSPENSION OF STUDY

This study may be temporarily suspended or prematurely terminated if there is sufficient reasonable cause. Written notification, documenting the reason for study suspension or termination, will be provided by the suspending or terminating party to the investigator. If the study is prematurely terminated or suspended, the PI will promptly inform the IRB and will provide the reason(s) for the termination or suspension.

Circumstances that may warrant termination or suspension include, but are not limited to:

- Determination of unexpected, significant, or unacceptable risk to participants
- Demonstration of efficacy that would warrant stopping
- Insufficient compliance to protocol requirements
- Data that are not sufficiently complete and/or evaluable
- Determination of futility

Study may resume once concerns about safety, protocol compliance, data quality are addressed and satisfy the PI and/or the IRB.

6 STUDY PROCEDURES AND SCHEDULE

6.1 STUDY PROCEDURES/EVALUATIONS

6.1.1 STUDY SPECIFIC PROCEDURES

- Study personnel will identify subjects who meet inclusion criteria and none of the exclusion criteria and approach them for informed consent to participate in the study.
- Once a subject agrees to participate, a brief obstetrical history will be obtained.
- If subjects' clinically indicated ultrasound study is normal, Doppler measurements of the umbilical and middle cerebral arteries will be obtained three times each and the mean value of the PI will be used to determine the CPR. Data will be recorded on study forms.
- The subject's medical record will be abstracted to obtain relevant data on study forms. Mode of delivery, whether this was a diagnosis of fetal compromise and managing physician's diagnoses will be obtained from the maternal chart. Birthweight, 1 and 5 minute Apgars scores, cord blood gasses (if done) and NICU admission will be recorded. The newborn birth record will also be reviewed for specific complications including need for supplemental oxygen, intracranial hemorrhage, hypoglycemia, jaundice, an unspecified complications.

6.1.2 STANDARD OF CARE STUDY PROCEDURES

Standard of care will not be impacted by a subjects' enrollment in the study. The only difference in care will be assessment of the middle cerebral and umbilical artery by Doppler in women who consent to participate in the study. Clinical care providers will be blinded to the Doppler results. There will be no involvement of study personnel on Labor and Delivery. All data recorded for maternal and neonatal outcomes will be obtained by chart abstraction after delivery has occurred.

6.2 LABORATORY PROCEDURES/EVALUATIONS

6.2.1 CLINICAL LABORATORY EVALUATIONS

With the exception of the Doppler measurements of the fetal middle cerebral and umbilical arteries, no additional assessment will be performed for subjects in the study. Data of laboratory results will be abstracted from the medical record. Specifically, umbilical artery and venous cord pH measurements will be recorded if they were performed by the clinical team as part of their routine obstetric care.

6.2.2 OTHER ASSAYS OR PROCEDURES

Not applicable.

6.2.3 SPECIMEN PREPARATION, HANDLING, AND STORAGE

6.2.4 SPECIMEN SHIPMENT

Not applicable.

6.3 STUDY SCHEDULE

6.3.1 SCREENING

Potential subjects will be approached to enroll in the study if they present to an obstetrical ultrasound unit at a participating site. If subjects meet inclusion criteria but not of the exclusion criteria they will be offered enrollment in the study and asked to sign an informed consent form if they agree to participate. They will have their ultrasound along with study Doppler measurements immediately following the consent process.

6.3.2 ENROLLMENT/BASELINE

When the study subject has her ultrasound, the fetus must not be growth restricted as defined by a composite EFW of less than the 10th percentile to continue participation in the study.

The ultrasound assessment of Doppler studies must be complete. If the sonographer cannot obtain satisfactory measurements of both vessels, this information will be recorded but additional subjects will need to be recruited to meet sample size requirements.

6.3.3 FOLLOW-UP

After study subjects deliver, maternal and neonatal charts will be reviewed and relevant study data will be abstracted.

6.3.4 FINAL STUDY VISIT

There is only a single study visit when the ultrasound Doppler measurements are obtained. All additional data will be obtained through chart abstraction.

6.3.5 EARLY TERMINATION VISIT

Subjects have the right to withdraw from the study at any point. No early termination visit will be required as all necessary procedures would have been performed during the solitary study visit.

6.3.7 SCHEDULE OF EVENTS TABLE

Procedures	Enrollment (Only Subject Visit)	Delivery Chart Abstraction	
Informed Consent	X		
Demographics	X		
Medical History			
Height			
Weight	X		
Middle Cerebral Artery Doppler	X		
Umbilical Artery Doppler	X		
CPR Calculation	X		
Maternal data		x	
Neonatal data		x	

6.4 JUSTIFICATION FOR SENSITIVE PROCEDURES

Not applicable.

6.5 CONCOMITANT MEDICATIONS, TREATMENTS, AND PROCEDURES

Not applicable.

6.5.1 PRECAUTIONARY MEDICATIONS, TREATMENTS, AND PROCEDURES

Not applicable.

6.6 PROHIBITED MEDICATIONS, TREATMENTS, AND PROCEDURES

Not applicable.

6.7 PROPHYLACTIC MEDICATIONS, TREATMENTS, AND PROCEDURES

Not applicable.

6.8 RESCUE MEDICATIONS, TREATMENTS, AND PROCEDURES

Not applicable.

6.9 PARTICIPANT ACCESS TO STUDY AGENT AT STUDY CLOSURE

Not applicable.

7 ASSESSMENT OF SAFETY

7.1 SPECIFICATION OF SAFETY PARAMETERS

Diagnostic ultrasound studies of the fetus are generally considered safe during pregnancy. The lowest possible ultrasonic exposure setting should be used to gain the necessary diagnostic information under the ALARA (as low as reasonably achievable) principle. The 3 additional measurements of the umbilical and middle cerebral arteries are not thought pose additional risk to the study subject or the fetus. There cannot be adverse events related to the study.

7.1.1 DEFINITION OF ADVERSE EVENTS (AE)

Not applicable.

7.1.2 DEFINITION OF SERIOUS ADVERSE EVENTS (SAE)

Not applicable.

7.1.3 DEFINITION OF UNANTICIPATED PROBLEMS (UP)

Not applicable.

7.2 CLASSIFICATION OF AN ADVERSE EVENT

7.2.1 SEVERITY OF EVENT

Not applicable.

7.2.2 RELATIONSHIP TO STUDY AGENT

Not applicable.

7.2.3 EXPECTEDNESS

Not applicable.

7.3 TIME PERIOD AND FREQUENCY FOR EVENT ASSESSMENT AND FOLLOW-UP

Not applicable.

7.4 REPORTING PROCEDURES

7.4.1 ADVERSE EVENT REPORTING

Not applicable.

7.4.2 SERIOUS ADVERSE EVENT REPORTING

Not applicable.

7.4.3 UNANTICIPATED PROBLEM REPORTING

Not applicable.

7.4.4 EVENTS OF SPECIAL INTEREST

Not applicable.

7.4.5 REPORTING OF PREGNANCY

All study subjects will be pregnant

7.5 STUDY HALTING RULES

Not applicable.

7.6 SAFETY OVERSIGHT

Study procedures will be reviewed by the common IRB at Columbia University and implemented by IRBs at other PRC sites.

8 CLINICAL MONITORING

Clinical site monitoring is conducted to ensure that the rights and well-being of human subjects are protected, that the reported trial data are accurate, complete, and verifiable, and that the conduct of the trial is in compliance with the currently approved protocol/amendment(s), with GCP, and with applicable regulatory requirement(s).

- A central webinar training for research staff will be performed for initial start-up of participating sites.
- A standardized Doppler measurement training will be required for sonographers prior to acquisition of measurements for the study.
- Target or random review of data will be performed remotely. The data will be sent coded and encrypted from each site to Rutgers- Robert Wood Johnson Medical School for the review.
- Independent audits will not be conducted.

9 STATISTICAL CONSIDERATIONS

9.1 STATISTICAL AND ANALYTICAL PLANS

Statistical analysis is expected to be straight forward in this study. Chi-square or the Fisher exact test will be used to compare binary outcomes. Continuous variables will be compared with the Student *t* test or Mann-Whitney test as appropriate.

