	pregnancies complicated by IUGR. The CPR may predict adverse outcomes in low risk pregnancies. In a prospective study, we will examine whether fetuses with an abnormal CPR at or near term are at increased risk for being delivered by cesarean
Objective	To assess whether women with appropriately grown fetuses in otherwise low risk pregnancies with an abnormal CPR are more likely to be delivered by cesarean section
Endpoints	
Primary outcome variable:	Cesarean for non-reassuring fetal heart tracings
Secondary outcome variables:	Total cesarean delivery rate Umbilical cord blood pH Unidentified small for gestational age births Birthweight percentile Prevalence of category 2 or 3 fetal heart tracings Distribution of CPR by EFW Rate of operative vaginal delivery NICU admission Apgar scores at 1 and 5 minutes Composite neonatal outcome
Population	Healthy women with low-risk pregnancies receiving care at study institutions
Number of Sites enrolling participants	8
Description of Study Agent	Prenatal ultrasound Doppler assessment of the umbilical and middle cerebral arteries
Study Duration	12 months
Participant Duration	Between 1 day and 6 weeks

SCHEMATIC OF STUDY DESIGN

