2.3.2 KNOWN POTENTIAL BENEFITS

Study subjects will not gain any benefit from enrolling in this observational study. Data gleaned from this work may be of benefit to pregnant women in the future.

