4 STUDY DESIGN AND ENDPOINTS

4.1 DESCRIPTION OF THE STUDY DESIGN

This is a multicenter prospective study of low-risk women who will be recruited if they are having an ultrasound at 36 weeks EGA or greater or if they are presenting to Labor and Delivery for induction of labor. As part of the study, women will have umbilical and middle cerebral artery Doppler studies and the CPR will be calculated by dividing the MCA PI by the UA/PI. Providers caring for study subjects will be blinded to this result. Pregnancy outcomes in women with CPR values less than the 10th percentile for gestational age will be compared to those with CPR values above the 10th percentile.

A secondary aim to our study is to analyze CPR as a continuous variable.

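### Section 9.1 fixes only unadjusted tests for a non-randomized comparison of CPR groups across eight sites, two entry routes and mixed parity; an adjusted estimate should be prespecified beside the crude one.

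*Protocol*

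**What the plan says.** Section 9.1 opens with "Statistical analysis is expected to be straight forward in this study". It then states that "Chi-square or the Fisher exact test will be used to compare binary outcomes", and assigns the Student t or Mann-Whitney test to continuous variables. No covariate, stratum or site term appears there or elsewhere in the protocol.

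The design is described as follows:

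- **Observational.** Section 2.3.2: "Study subjects will not gain any benefit from enrolling in this observational study".
- **Groups set by measurement.** Section 4.1: "Pregnancy outcomes in women with CPR values less than the 10th percentile for gestational age will be compared" with outcomes in the remaining women.
- **Eight sites.** The synopsis gives 8 under "Number of Sites enrolling participants".
- **Two entry routes.** Section 4.1 recruits women having an ultrasound at 36 weeks or later, "or if they are presenting to Labor and Delivery for induction of labor".
- **Mixed parity.** Section 5.2 excludes prior cesarean but does not restrict parity.

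On what is recorded, section 6.1.1 says only that "a brief obstetrical history will be obtained", and the schedule in 6.3.7 marks demographics and weight at enrollment. Site is identifiable, because section 8 says "The data will be sent coded and encrypted from each site". Parity is not named, and no section lists entry route as a recorded item.

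**The concern.** A chi-square test treats all 3,000 women as one exchangeable sample. If parity, entry route or site practice affects cesarean risk and is also related to CPR or its measurement, the crude contrast mixes that relation with any CPR effect. The mixing can act in either direction: it can produce a difference where CPR does nothing, or shrink a real one.

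This matters for how the result will be used. Section 2.2 hopes that CPR will lead to better strategies for reducing cesareans. A reader will want to know whether a low CPR carries information beyond a woman's parity, her reason for being scanned and the hospital where she delivers. The tests in section 9.1 cannot answer that.

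**Working it through.** **1. The protocol's own figure.** Inputs from section 9.5: 20% v 10% cesarean, 90% power, alpha 0.05 (taken as two-sided). The equal-group two-proportion formula gives 266 per group, or 286 with continuity correction. The stated 288 is therefore reproduced closely, as an unadjusted calculation with equal groups. The split in section 5.3 is about 300 v 2,700. At that split, power for 20% v 10% is 99.6%, and power is already about 90% for 16.5% v 10%. A modest difference, confounded or real, can therefore reach significance.

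**2. A spurious difference.** Assumptions, none of them from the protocol: 45% nulliparous; cesarean risk r1 in nulliparous and r0 in parous women; no CPR effect within parity; low-CPR prevalence a in nulliparous and b in parous women, chosen to give about 10% overall.

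- Overall low-CPR share: L = 0.45a + 0.55b.
- Nulliparous share: f_low = 0.45a/L in the low-CPR group and f_norm = 0.45(1 − a)/(1 − L) in the others.
- Crude risk in each group: f·r1 + (1 − f)·r0.
- Rejection probability: Φ((d − 1.96·SE0)/SE1) + Φ((−d − 1.96·SE0)/SE1), where d is the risk difference, SE0 the pooled and SE1 the unpooled standard error at 300 v 2,700.

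Example, r1 = 18%, r0 = 5%, a = 13%, b = 7.6%:

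- L = 0.0585 + 0.0418 = 0.1003.
- f_low = 0.0585/0.1003 = 0.583; f_norm = 0.3915/0.8997 = 0.435.
- Crude risks 12.6% v 10.7%, ratio 1.18.
- d = 0.0193, SE0 = 0.0189, SE1 = 0.0200, so rejection is 0.19.

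| Cesarean, nulliparous v parous | Low-CPR prevalence, nulliparous v parous | Crude risks, low v normal CPR | Crude RR | Rejection |
|---|---|---|---|---|
| 18% v 5% | equal (10% each) | 10.9% v 10.9% | 1.00 | 5% |
| 18% v 5% | 11% v 9.2% | 11.4% v 10.8% | 1.06 | 7% |
| 18% v 5% | 12% v 8.4% | 12.0% v 10.7% | 1.12 | 11% |
| 18% v 5% | 13% v 7.6% | 12.6% v 10.7% | 1.18 | 19% |
| 20% v 4% | 14% v 6.7% | 14.1% v 10.9% | 1.30 | 40% |

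**3. A masked effect.** Assume a risk factor with cesarean risk 15% v 5%, present in 40% of normal-CPR women, and a true within-stratum ratio of 1.5. The normal-CPR risk is 0.4 × 15% + 0.6 × 5% = 9%. If the factor is present in only 20% of low-CPR women, their risk is 1.5 × (0.2 × 15% + 0.8 × 5%) = 10.5%. The observed ratio is 1.17 and power is 15%. With no imbalance the figures are 13.5% v 9%, ratio 1.5 and power 69%.

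**4. Site alone.** In a simulation of 8 sites with 375 women each and independent site variation (assumed SD 0.4 and 0.5 on the logit scale), the chi-square type I error was 5.8% and 7.4%. A Cochran-Mantel-Haenszel test gave 5.4% and 4.7%. Site by itself is a small problem under these assumptions.

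**5. Can the sample carry adjustment?** Expected cesareans: 300 × 20% + 2,700 × 10% = 60 + 270 = 330. The parameters are CPR, parity, entry route, maternal age, weight and seven site terms, 12 in all, so 330/12 = 27.5 events each. For power, the log odds ratio is ln(0.2 × 0.9/(0.1 × 0.8)) = 0.811, with variance 1/(300 × 0.16) + 1/(2,700 × 0.09) = 0.0250. Wald power is 99.9%. With the variance inflated by 1/(1 − R²) for R² = 0.20 between CPR group and covariates, it is 99.6%.

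**The case against.** The strongest reply is that the stated aim is prediction (sections 2.2 and 3). For that aim a crude contrast is a legitimate first estimate of the marginal association. This stands, and it is why the crude test should be kept. It does not cover a claim that CPR has an effect independent of known factors.

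A second reply is that section 9.1 only matches tests to variable types, and that a separate analysis plan could add a model. The absence of a covariate list is indeed no error. But the protocol does state a method, and a plan that followed it would be unadjusted.

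Several stronger readings are tempting and are not supported:

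- *The needed covariates are already collected.* Site and gestational age at scan must be known, and demographics and weight are scheduled. Parity is only implied by the obstetrical history, and entry route is not listed.
- *Gestational age is uncontrolled.* The cut-off is specific for gestational age, so gestational age at the scan is already partly handled.
- *Adjustment will raise power.* That is not assured in a non-randomized cohort, where covariates related to CPR inflate the variance. Crude power is ample at the planned effect in any case.
- *The planned doubling could be pure confounding.* No null scenario examined gives that. Among further null scenarios, the largest crude ratio was 1.46, with a risk factor (25% v 5% cesarean risk) in 70% of low-CPR and 40% of other women.

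It is also fair to say that nothing in the protocol shows parity to be related to CPR, and that the Doppler training required in sections 8 and 11 should limit measurement differences between sites.

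**Conclusion.** The point holds in limited form. Section 9.1 fixes only crude tests for groups that are not randomized, in a cohort mixed by site, entry route and parity. A cesarean difference could therefore reflect or be masked by those factors. Neither the size nor the direction of the bias can be derived from the protocol. Under the assumed parity scenarios the false-positive rate runs from the nominal 5% with no imbalance, through 7% to 19% with mild to moderate imbalance, to 40% with a strong gradient, at crude ratios of 1.00 to 1.30. The realistic risk is a false or distorted modest association, not a spurious doubling. This should be corrected, but it does not invalidate the crude comparison as a description.

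**What to change.** Keep the crude comparison as the estimate of the marginal association. Beside it, prespecify a logistic or modified Poisson regression of the primary outcome on CPR below the 10th percentile, with parity, entry route, maternal age, weight and site. Report the adjusted risk ratio and risk difference with 95% confidence intervals, and state that any claim of an independent CPR effect rests on the adjusted result.

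If events are few, use a Cochran-Mantel-Haenszel analysis stratified by site and parity instead. This could arise if the endpoint is cesarean for non-reassuring tracings only, as in the synopsis, and not all cesareans, as in section 4.2.1. The count of 330 events applies to all cesareans at the rates in section 9.5.

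Name parity and entry route explicitly on the data form.

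The cost is two data-form fields, a few sentences of protocol or analysis-plan text and a little more programming. Women already enrolled may need the two items abstracted from their charts. No additional enrollment is required.
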